# 7.7. Study and Site Closure

Both the Sponsor and the Investigator reserve the right to terminate the study at any time. Should this be necessary, both parties will arrange discontinuation procedures. In terminating the study, the Sponsor and the Investigator will assure that adequate consideration is given to the protection of the subjects' interests.

Upon completion of the study, the monitor will conduct the following activities in conjunction with the Investigator or site staff, as appropriate:

Return of all study data to the Sponsor (as applicable)

Resolution of all data queries

Accountability, reconciliation, and arrangements for all unused GC4419/Placebo

Review of site study records for completeness

Shipment of laboratory samples (as applicable)

In addition, the Sponsor reserves the right to temporarily suspend or prematurely discontinue this study either at a single site or at all sites at any time for reasons including, but not limited to, safety or ethical issues or severe non-compliance. If the Sponsor determines such action is needed, the Sponsor will discuss this with the Investigator (including the reasons for taking such action) at that time. When feasible, the Sponsor will provide advance notification to the Investigator of the impending action prior to it taking effect.

The Sponsor will promptly inform all other investigators and/or institutions conducting the study if the study is suspended or terminated for safety reasons and will also inform the regulatory authorities of the suspension or termination of the study and the reason(s) for the action. If required by applicable regulations, the Investigator must inform the IRB/IEC/Research Ethics Board (REB) promptly and provide the reason for the suspension or termination. If the study is prematurely discontinued, all study data must be returned to the Sponsor.

Financial compensation to investigators and/or institutions will be in accordance with the agreement established between the Investigator and the Sponsor.

#### 8. GC4419/PLACEBO

## 8.1. Description of GC4419/Placebo

#### 8.1.1. GC4419

GC4419 (Manganese,dichloro[(4aS,13aS,17aS,21aS)-1,2,3,4,4a,5,6,12,13,13a,14,15,16,17,17a,18,19,20,21a-eicosahydro-11,7-nitilo-7H-dibenzo[b,h][1,2,7,10]tetraazacylcoheptadecine-κN5,κN13,κN18,κN21,κN22]-) is a water soluble, highly stable, low molecular weight manganese-containing macrocyclic ligand complex whose activity mimics that of naturally occurring SOD enzymes.

GC4419 is formulated as a clear solution at the following concentration to support the active arm:

Arm A: 90 mg GC4419: 9 mg/mL in 26 mM sodium bicarbonate-buffered 0.9 wt. % saline for parenteral administration.

Galera Therapeutics, Inc.

Version: Amendment 4

There are no other excipients. GC4419 is packaged as a 11 mL  $\pm$  0.1mL aliquot in a 10 mL amber glass vial with an S-127 4432/50 gray stopper and a 20 mm red flip-off seal.

#### **8.1.2.** Placebo

Arm B: 26 mM sodium bicarbonate-buffered 0.9 wt. % saline for parenteral administration.

There are no other excipients. Placebo is packaged as a clear solution of  $11 \text{ mL} \pm 0.1 \text{mL}$  aliquot in a 10 mL amber glass vial, with an S-127 4432/50 gray stopper and a 20 mm red flip-off seal.

# 8.2. Treatment Assignment

Subjects will be randomly assigned to one of the two treatment arms through an interactive response technology (IRT). The system will assign a subject a unique randomization number that will remain consistent for the duration of the study. See the Pharmacy Binder for additional information regarding subject randomization and the IRT system.

## 8.2.1. Blinding

Treatment assignment should remain blinded until analyses of the primary and secondary safety and efficacy results of the study have been performed on the final, locked data through the end of post-IMRT follow-up for all subjects. Only in the case of an emergency, when knowledge of the investigational product is essential for the clinical management or welfare of the subject, may the Investigator unblind an individual subject's treatment assignment prior to the completion of the primary and secondary safety and efficacy analyses. The Investigator will, whenever possible, discuss options with the Medical Monitor or appropriate Sponsor/CRO study personnel before unblinding. If the blind is broken for any reason and the Investigator is unable to contact the Sponsor prior to unblinding, the Investigator must notify the Sponsor/CRO as soon as possible following the unblinding incident without revealing the subject's study treatment assignment, unless the information is important to the safety of subjects remaining in the study.

If a serious adverse event (SAE; as defined in Section 11.1.2) is reported to the Sponsor/CRO, the Sponsor/CRO staff may unblind the treatment assignment for the individual subject. If an expedited regulatory report to one or more regulatory agencies is required, the report will identify the subject's treatment assignment, consistent with applicable regulations for the territory in which the report is made. When applicable, a copy of the regulatory report may be sent to investigators in accordance with relevant regulations, the Sponsor policy, or both.

## 8.3. GC4419/Placebo Packaging and Labeling

GC4419 and Placebo will be presented in kits of 35 single-use vials, which represent 35 daily doses to be administered IV concurrent with IMRT. To maintain the blind, GC4419, as well as Placebo, will be packaged into amber vials and will appear generally identical; that is, there will be no distinguishing features in or on the packaging that could permit the identification of GC4419 or Placebo.

#### 8.3.1. GC4419

GC4419 is packaged as an 11 mL  $\pm$  0.1mL aliquot in a 10 mL amber glass vial with a S-127 4432/50 gray stopper and a 20 mm red flip-off seal. Each bottle will be labeled with the appropriate language, including the required regulatory text. Further label details will be provided in a separate Pharmacy Manual.

Galera Therapeutics, Inc.

Version: Amendment 4

#### 8.3.2. Placebo

Placebo is packaged as an  $11 \text{ mL} \pm 0.1 \text{mL}$  aliquot in a 10 mL amber glass vial with an S-127 4432/50 gray stopper and a 20 mm red flip-off seal. Each bottle will be labeled with the appropriate language, including the required regulatory text. Further label details will be provided in a separate Pharmacy Manual.

## 8.4. GC4419/Placebo Storage

GC4419/Placebo must be stored at 2°C to 8°C at all times until use. Study drug must not be frozen at any time. Temperature excursions up to 25°C or down to 0.1°C for four hours are accepted; however, the Sponsor or its designee must be notified immediately of the temperature excursion to ensure proper oversight.

Once prepared, the IV bags containing GC4419/Placebo saline mixtures must be administered to subjects within 24 hours. GC4419/Placebo saline mixtures should spend as little time as possible outside refrigerated conditions, not exceeding more than 6 hours at ambient temperature, and must never be frozen. If freezing of the material is evident, that supply must be quarantined per institutional guidelines and the Sponsor or its designee must be notified immediately.

## 8.5. GC4419/Placebo Preparation

GC4419/Placebo will be provided to the study site in single use, sterile, pyrogen-free vials ready for dose preparation. Proper mixing with normal saline is required. Standard aseptic techniques will be used to maintain sterility.

Assignment of treatment arm will be randomized 3:2 with respect to treatment arms A and B. GC4419 and Placebo will be presented in kits of 35 single-use vials, which represent 35 daily doses to be administered IV concurrent with IMRT.

To prepare daily IV solutions, investigational pharmacists will extract 10 mL from a single vial and add to 250 mL normal saline. Note that there is no extraction of saline (i.e., the infusion solution volume will be 250 mL saline + 10mL volume of GC4419/Placebo for a total volume of 260 mL). No additional modifications or adjustments are to be made to the infusion solution.

The GC4419 solution may appear clear or have a slight yellowish tint. Although solutions should be free of particulates, it is possible that some vials may have some fine visible particulates. Infusions must be prepared using a sterile 0.2 or 0.22 micron syringe filter prior to introduction into the infusion bag or a sterile 0.2 or 0.22 micron inline filter must be used during IV administration. Filtration does not influence dosage calculations.

NOTE: Filtration is mandatory, either during preparation with syringe filters or at IV administration with inline filters. Unfiltered GC4419 solution or infusion solution must not be administered to patients.

Further information and preparation details will be provided in a separate Pharmacy Manual.

Note: Investigational staff who prepare infusion solutions cannot be oral evaluators. Any investigational staff that prepare infusions should maintain a strict blind of treatment assignment. In the event a vial contains particulates or is discolored with a slight yellowish tint that could indicate active drug, such an unblinded observation should not be discussed with internal site staff including those that may be directly involved in subject assessments.

Galera Therapeutics, Inc.

Version: Amendment 4

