## 5.2. Endpoints

### **Primary Endpoint:**

Cumulative incidence of SOM, defined as the proportion of subjects with any occurrence of WHO Grade 3-4 OM, during the Study Treatment Period

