Many reports of OM in clinical studies use the NCI-CTCAE, in which the grading of OM is different from the WHO scale (Table 2). Whereas the WHO criteria have been stable for years, NCI criteria have changed markedly with every new version. The NCI criteria have found their greatest application in describing mucositis as an AE associated with anti-cancer regimens, not as an instrument to assess intervention efficacy.

Table 2: Comparison of WHO Scale vs. NCI-CTCAE v5.0 for Oral Mucositis

OM Grade	WHO Scale	NCI-CTCAE v5.0
0	No mucositis	No mucositis
1	Pain and erythema	Asymptomatic or mild symptoms; intervention not indicated
2	Ulceration but no compromise in diet (able to eat solid food)	Moderate pain or ulcer that does not interfere with oral intake; modified diet indicated
3	Ulceration with ability to eat only liquids	Severe pain; interfering with oral intake
4	Ulceration with inability to eat/requirement for tube or parenteral feeding	Life-threatening consequences; urgent intervention indicated

As noted, the WHO scale will be used in the current study. Separate grading of OM according to the NCI-CTCAE will not be performed. As in prior Galera-sponsored studies (GT-001 and GT-201), the WHO OM score for each subject will be assessed by trained Investigator-evaluators followed by Quality Control process as described under GT-201 results (See Investigator's Brochure).

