#### 8.6. GC4419/Placebo Administration

GC4419 or Placebo/saline mixture will be administered intravenously at an infusion rate that totals 60 min (± 6 min to account for saline overfill) for the total dose assigned. Infusions of GC4419/Placebo must be administered using an infusion pump (i.e., not by drip rate). Infusion pump models are not specified and may be per institutional preference/standard. If sterile 0.2 or 0.22 micron syringe filters are not used during infusion preparation, 0.2 or 0.22 micron inline filters must be used during IV administration.

To facilitate administration of GC4419/Placebo according to the study schedule, an indwelling venous access device may be used, at the discretion of the treating Investigator.

IMRT must be initiated as soon as possible upon completion of the GC4419/Placebo infusion, but no later than 60 minutes following the end of the infusion.

GC4419/Placebo will be given beginning on the first day of radiation and continuing daily, concurrent with each dose of IMRT, to a cumulative radiation dose of approximately 60-72 Gy.

Table 3 outlines the chemoradiation and GC4419/Placebo administration schedules. Please note chemotherapy is not required to be administered on the study days listed in Table 3 as long as it follows a weekly or tri-weekly schedule.

If IMRT is not administered on any given day due to a treatment break or unforeseen circumstances, GC4419/Placebo should not be administered on that day. Breaks in IMRT will be determined by the subject's treating physician in accordance with standard of care. Subjects should resume GC4419/Placebo administration when IMRT resumes. On days when planned doses of both GC4419/Placebo and IMRT are not administered (e.g., due to a holiday site closure), GC4419/Placebo dosing may be extended along with IMRT to make up the missed dose(s) to a maximum of 35 doses of GC4419/Placebo. If a fraction of IMRT is not administered for any reason after GC4419/Placebo has been administered, that day's GC4419/Placebo will count as one of the 35 doses.

Table 3: Chemoradiation and GC4419/Placebo Administration Schedule Example: 35 Doses of GC4419/Placebo (5 days/week over 7 Week Schedule)

Treatment	Week 1				Week 2				Week 3				Week 4							
	Day	Day	Day	Day	Day	Day	Day	Day												
	1	2	3	4	5	8	9	10	11	12	15	16	17	18	19	22	23	24	25	26
GC4419/Placebo 	X	X	X	X	X	X	X	X	X	X	X	X	X	X	X	X	X	X	X	X
Cisplatin 																				
Tri-Weekly	X															X				

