For subjects receiving weekly cisplatin, record BSA (used to confirm cisplatin dosing)

Measure body weight

Record tobacco use

Draw blood for laboratory measurements

- Chemistry profile
- Hematology profile

Administer GC4419/Placebo doses by continuous intravenous infusion. IMRT must begin as soon as possible but no later than 60 minutes following the end of GC4419 dosing.

### 10.9.6. Week 4

Prior to GC4419/Placebo administration the following observations and procedures will be conducted for all subjects on all IMRT days:

Record changes to concomitant medications

Record AEs

Prior to IMRT administration the following procedure will be conducted for all subjects twice during this week, at least two days apart:

Conduct OM assessment and record the severity using the WHO score

Prior to GC4419/Placebo administration the following observations and procedures will be conducted for all subjects once this week:

Perform symptom-directed PE

Measure vital signs, body weight, and ECOG Performance Status

Record BSA (used to confirm chemotherapy dosing)

Record tobacco use

Draw blood for laboratory measurements

- Chemistry profile
- Hematology profile
- Cotinine test
- Biomarker sample for pro-inflammatory cytokine analysis (See Section 10.5)

Galera Therapeutics, Inc.

Version: Amendment 4

Prior to GC4419/Placebo administration the following observations and procedures will be conducted for all subjects on Day 22 only:

Draw blood for PK sampling (See Section 10.4)

Measure blood pressure within 30 minutes prior to pre-GC4419/Placebo Infusion PK blood draw (See Section 10.1.1)

Administer GC4419/Placebo doses by continuous intravenous infusion.

Following GC4419/Placebo administration the following observations and procedures will be conducted for all subjects on Day 22 only:

Measure blood pressure (See Section 10.1.1)

Draw blood for PK sampling (See Section 10.4)

IMRT must begin as soon as possible but no later than 60 minutes following the end of GC4419 dosing.

#### 10.9.7. Week 5

Prior to GC4419/Placebo administration the following observations and procedures will be conducted for all subjects on all IMRT days:

Record changes to concomitant medications

Record AEs

Prior to GC4419/Placebo administration the following procedure will be conducted for all subjects twice during this week, at least two days apart:

Conduct OM assessment and record the severity using the WHO score

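### Blinding of oral mucositis grading: the bar on graders stops at infusion preparers, grading may follow the infusion in Weeks 4, 6 and 7, and SAE unblinding is not stated to be separate from score quality control

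*Combined protocol and SAP*

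**What the plan says.** - **Signal.** Section 8.5 says GC4419 solution may be clear or faintly yellow and that some vials may hold fine particulates. It treats a vial that contains particulates or is "discolored with a slight yellowish tint that could indicate active drug" as an unblinding observation. Section 8.1.2 describes placebo only as clear.
- **Safeguards.** Section 8.5 states: "Investigational staff who prepare infusion solutions cannot be oral evaluators". It also tells preparers to keep a strict blind and not to share such an observation with site staff, assessors included. Section 8.3 specifies amber vials and says "there will be no distinguishing features in or on the packaging that could permit the identification of GC4419 or Placebo".
- **Filter and bag.** Filtration is mandatory, but a site may skip the syringe filter, in which case "0.2 or 0.22 micron inline filters must be used during IV administration" (Section 8.6). Ten mL from the vial goes into 250 mL of saline, 260 mL in all. No cover for bag or line is required.
- **Timing.** Section 10.9.6 (Week 4) introduces the oral mucositis (OM) assessment with "Prior to IMRT administration the following procedure will be conducted for all subjects"; Sections 10.9.8 and 10.9.9 (Weeks 6 and 7) do the same. The other treatment weeks and the last-day visit place it before study drug.
- **Unblinding.** Under Section 8.2.1, once a serious adverse event (SAE) is reported, "the Sponsor/CRO staff may unblind the treatment assignment for the individual subject". Expedited reporting is the subject of the next sentence, not a condition on this one. The section also sets a general blind until the primary and secondary analyses are done.
- **Score review.** Section 5.2.1 says each WHO score "will be assessed by trained Investigator-evaluators followed by Quality Control process", and refers to the Investigator's Brochure for the process.
- **Endpoint.** Section 5.2: "Cumulative incidence of SOM, defined as the proportion of subjects with any occurrence of WHO Grade 3-4 OM, during the Study Treatment Period".

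**The concern.** The line between Grade 2 and Grade 3 on the WHO scale turns on whether a subject with ulcers can eat solids or only liquids. That is a trained evaluator's judgement, based partly on what the subject reports. A grader who suspects the arm can lean on borderline calls, and those calls feed directly into the primary endpoint.

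The protocol concedes that the product may give the arm away, then guards against one role only. Someone who hangs or monitors the bag may also be the grader, and in three of the seven treatment weeks may grade after that day's infusion. Separately, Sponsor/CRO staff may learn assignments more often than reporting rules require, and nothing written keeps those staff away from the score review.

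Appendix 8 says the enlarged sample is meant to support a marketing application on a single pivotal efficacy study, so credibility of the blind carries unusual weight.

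**Working it through.** **1. Who is covered (Sections 8.3, 8.5, 8.6)**

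| Role | Barred from grading OM | Told to keep a strict blind | Bag or line masked |
|---|---|---|---|
| Prepares the infusion | Yes | Yes | Not applicable |
| Hangs or monitors the infusion | No rule | No rule | No rule |

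The no-discussion rule concerns what is seen in the vial. It limits what a preparer passes on, not what another person sees first-hand. With an inline filter, the solution in the bag has not yet been filtered. Against this, the dilution is 260/10 = 26-fold, and no section says whether tint or particulates can be seen in the bag.

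**2. When grading happens**

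| Period | Section | OM assessment must precede |
|---|---|---|
| Week 1 | 10.9.1, 10.9.3 | Study drug |
| Weeks 2, 3 | 10.9.4, 10.9.5 | Study drug |
| Week 4 | 10.9.6 | IMRT only |
| Week 5 | 10.9.7 | Study drug |
| Weeks 6, 7 | 10.9.8, 10.9.9 | IMRT only |
| Last day of IMRT | 10.9.10 | Study drug |

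Study drug is infused over 60 minutes and IMRT follows within 60 minutes of its end. A requirement to grade before IMRT therefore permits grading during or after the infusion. No reason for the difference is given.

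**3. Sponsor/CRO side.** Permission to unblind attaches to any reported SAE, and no designated group is named. Section 5.2.1 does not say who performs score quality control, whether they are blinded, or whether they can change a score.

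**4. The plan's own figure.** Section 12.2 gives 65% vs 43%, 144 placebo and 216 GC4419 subjects, and about 95% power; Section 12.5 gives two-sided alpha 0.05. With the usual two-proportion approximation:

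- power = Φ[(d − 1.96·SE0)/SE1], where SE0 = √[p̄(1−p̄)(1/144 + 1/216)] and SE1 = √[p1(1−p1)/144 + p2(1−p2)/216]
- p̄ = (144×0.65 + 216×0.43)/360 = 0.518; SE0 = 0.0538; SE1 = 0.0521
- power = Φ[(0.22 − 0.1054)/0.0521] = Φ(2.20) = 98.6%

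This is above the stated 95%, so the plan's figure is conservative. The difference has no bearing on this point.

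**5. Illustration of sensitivity.** Assume no true effect (65% in both arms) and that a share f of GC4419 subjects with severe OM (SOM) is graded below Grade 3 throughout. The documents give no value for f. Then p2 = 0.65(1 − f), and the same formula gives the chance of a significant result favouring GC4419.

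| f | Subjects regraded (216×0.65×f) | p2 | Chance |
|---|---|---|---|
| 0 | 0 | 65.0% | 2.5% |
| 5% | 7 | 61.75% | 9.0% |
| 10% | 14 | 58.5% | 23.4% |

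For f = 5%: d = 0.0325, SE0 = 0.0519, SE1 = 0.0517, and Φ[(0.0325 − 0.1018)/0.0517] = Φ(−1.34) = 9.0%. With 160 vs 240 subjects the last two chances are 9.6% and 25.5%. The calculation is unstratified, whereas the planned test is a stratified CMH test.

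**The case against.** Much of the case on the other side stands, and it rules out several stronger readings that a reader might infer.

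- **That the bag reveals the arm at the bedside.** Not shown. Tint is slight, not constant, and described in the vial. The inline-filter option means particulates could be in a bag, not that anyone would notice fine ones.
- **That infusion hypotension gives the arm away.** No between-arm difference is reported. Sections 4.2 and 6.2.1 describe safety at 90 mg in the earlier randomised study as similar to placebo.
- **That unblinded Sponsor staff influence scores.** No section says the same people do both jobs. The quality-control process is in the Investigator's Brochure and the SAE reporting instructions are in a separate manual; neither is available here. Only the absence of a written separation in these documents can be asserted.
- **That SAE unblinding falls mainly on subjects with severe OM.** Section 11.2.4 says OM is not reported as an adverse event. Complications could still generate an SAE, but how often is not given.
- **That one shifted visit changes a subject's outcome, so that a set share of the planned 22-point effect is at risk.** The endpoint is any Grade 3-4 score. Section 4.1.1 puts median onset at days 28-35 and median duration at 3-4 weeks, and Table 3 ends on Day 47. That leaves 12 to 19 days, or about 3 to 5 twice-weekly visits, and all of a subject's Grade 3-4 scores would have to be downgraded. A brief or late episode could rest on one score, but the documents do not say how common that is.

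Section 10.2 also calls for trained evaluators, fixed food definitions and as few evaluators per subject as possible. These measures reduce the risk. They do not address a grader who has handled the infusion.

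**Conclusion.** The point holds as an avoidable risk of assessor bias, not as evidence that the endpoint is biased. Three facts are established: the grading bar covers preparers only; grading may follow the infusion in Weeks 4, 6 and 7; and Sponsor/CRO unblinding is permitted after any SAE with no written separation from score quality control. Bedside visibility and overlap of staff are neither established nor excluded.

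The size of any bias cannot be estimated from the documents. The rise from 2.5% to about 9% or 23% shows only how few systematic regradings would matter. It rests on assumed regrading shares, a null effect at 65%, and complete downgrading of the affected subjects. Because the remedy is cheap, the change should be made.

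**What to change.** 1. **Section 8.5:** extend the bar so that staff who prepare, hang or monitor a subject's infusion do not grade that subject's OM. Where a site cannot separate these roles, cover the bag and line after the pharmacy's visual check.
2. **Sections 10.9.6, 10.9.8 and 10.9.9:** place the OM assessment before GC4419/Placebo, as in the other weeks. Because infusions are daily, this reduces same-day exposure only.
3. **Section 8.2.1:** limit Sponsor/CRO unblinding to SAEs that need an expedited report, carried out by designated safety staff with no role in OM score quality control or analysis. Leave emergency unblinding by the investigator unchanged. State that score quality control is blinded.

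**Cost:** amendment wording, covers and a safety-unblinding procedure. No extra assessor or change in sample size is needed. Some sites must reassign who grades a subject while respecting the fewest-evaluators rule, and a cover limits visual checks of the bag at the bedside.
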